After obtaining consent, the patient and his family will be given a sheet providing the office number, paging number, and cell phone for the PI and instructions on how to contact the PI. We will provide the patient and his family any information obtained from the QuadTw measurements, and will provide them with information as to whether the measured numbers are normal or reduced. If any complaints are registered by a subject these will be recorded and placed in the patient's study file. This information will be handled in a confidential matter (see above).

Does your research involve **Non-English Speaking Subjects or Subjects from a Foreign Culture**?

Yes  No

Non-English Speaking Subjects or Subjects from a Foreign Culture

Describe how information about the study will be communicated to potential subjects appropriate for their culture, and if necessary, how new information about the research may be relayed to subjects during the study.

Include contact information for someone who can act as a cultural consultant for your study. The person should be familiar with the culture of the subject population and/or be able to verify that translated documents are the equivalent of the English version of documents submitted. The consultant should not have any direct involvement with the study. If you do not know someone who would be willing to act as your cultural consultant, the Office of Research Integrity will try to find someone to fill this role (this may delay the approval process for your protocol). Please include the name, address, telephone number, and email of the person who will act as the cultural consultant for your study. For more details, see the IRB Application Instructions on [Research Involving Non-English Speaking Subjects or Subjects from a Foreign Culture](#).

For recruitment of Non-English speaking subjects, the consent document needs to be in the subject's native language. Download the informed consent template available in the E-IRB "Informed Consent/Assent Process" section and use it as a guide for developing the consent document. (Note: Your translated consent document can be attached to your application in the "Informed Consent" section; **be sure to save your responses in this section first.**)

If research is to be conducted at an international location, identify local regulations, laws, or ethics review requirements for human subject protection. If the project has been or will be reviewed by a local Ethics Committee, attach a copy of the review to the UK IRB using the attachment button below. You may also consult the current edition of the [International Compilation of Human Research Standards](#)

Does your study involve **HIV/AIDS research and/or screening for other reportable diseases (e.g., Hepatitis C, etc...)?**

Yes  No

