Unfortunately, there is currently no specific defined treatment to prevent or reverse muscle weakness in mechanically ventilated patients. Some recent work suggests that vigorous physical therapy, involving cycling exercise of ICU patient, may improve outcomes (3). Such treatments are labor intensive, however, and few ICU's currently have the manpower or equipment to provide such treatments. In addition, many MICU patients require significant sedation and are too obtunded to realistically participate in any active exercise training regimen. In the University of Kentucky MICU patients are supposed to receive 3 treatments of passive range of motion by physical therapists a week, but compliance with this regimen is poor and only a small minority of patients receive even this modest level of therapy. This minimal level of physical exercise for bed bound ICU patients is typical for patients across the country, with the result that many patients who walk into hospitals need to leave in wheel chairs. Depending upon their health insurance status, some of these patients receive outpatient rehabilitation, but many receive little or no therapy even after hospital discharge.

Recently, a number of companies have developed electrical stimulation devices that can exercise the quadriceps, the major leg muscle, by stimulating this muscle to rhythmically contract. This newer technology represents an advance over older electrical stimulators which can be extremely painful and produce potentially injurious robot-like muscle contractions. Currently this technique is being used to provide rehabilitation to leg muscles after knee surgery in orthopedic patients. The purpose of the present study is to use one of these newer stimulators, the All-Stim 2, in mechanically ventilated MICU patients to provide a means of safely, nonvolitionally exercising the leg muscles of these patients. We postulate that this form of treatment will increase leg muscle strength in these patients, reduce the duration of hospitalization, improve long term mobility, and reduce indices of long term disability.

**Objectives:** List your research objectives. You may reference grant application/sponsor's relevant protocol pages and attach as an appendix in the E-IRB "Additional Information" section, however, a summary paragraph must be provided in the text box below.

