which 45 Hz frequency current is used, with an on duration of 1 second and an off duration of 3 seconds; current intensity will be increased until the force generated by the quadriceps is 60% of the force generated by the quadriceps in response to magnetic twitch stimulation during the prior preliminary strength testing. (We have performed preliminary tests in normal individuals indicating that this level of force activation is well tolerated and produces a demonstrable reproducible submaximal quadriceps contraction). Once this current intensity is identified, all subsequent training trials will use this level of current density for training studies. Sham training will be performed with a setting of zero current intensity. Stimulation will be carried out as a single session per day with each session lasting 30 minutes.

**Initial Clinical Parameters:** These parameters will be obtained from the medical record using values collected as closely as possible to the time at which initial QuadTw physiological data measurements are made. Parameters will include age, sex, diagnoses, medications, reason for institution of mechanical ventilation, vital signs at the time of the initial visit, bedside parameters of mechanical ventilation use (including mode of ventilation, duration of ventilation, level of oxygen, breath volume and rate, % triggered breaths), most recent arterial blood gas values, and chest radiograph readings. To provide an assessment of pre-hospital function, family members will be asked four questions: (a) how far could the patient ambulate, (b) how many flights of steps could the patient go up, (c) which activities of daily living (dressing, carrying objects, performing daily grooming tasks), if any, were impaired, and (d) did the patient have difficulty standing from a sitting position or lifting objects over their head.

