To monitor the long term conduct of the study, including monitoring of adverse effects, we will employ a study monitoring board consisting of [name] and [name]. [name] is a well recognized epidemiologist with a background in statistics and his expertise will be used to make the appropriate statistical analysis of the data obtained from these studies. [name] is the Division Chief of Pulmonary/Critical Care Medicine who has had experience in physician compliance with ICU procedures and monitoring of patient safety in the conduct of invasive ICU procedures and he will have responsibility for assessment of safety issues. This board will review the study at twelve month intervals. At these meetings the board will evaluate the quality of the collected data, completeness of data collected for each patient studied, will review the eligibility form to assess compliance with inclusion/exclusion criteria, reporting of adverse effects by patients or nurses, will determine if the study should be continued or terminated because of safety/risk issues, and, at the final meeting, will review the final results.

Adverse effects will be recorded on study forms and reviewed by the DSMB. The DSMB will consider stopping the study if they conclude that excessive adverse effects clearly linked to one of the treatment arms are occurring. The board will compile a report for each meeting and present their findings to the PI.

To date there have been no adverse events..

No studies have been conducted in the last year so no DSMB assessment of the study has been performed since the last submission of this protocol. We will submit data to the DSMB once new subjects have been recruited.

[Back to Top](#)

**Subject Complaints:** Describe procedures (other than information provided in consent document) for handling subject complaints or requests for information about the research. The procedures should offer a safe, confidential, and reliable channel for current, prospective, or past research subjects (or their designated representative) permitting them to discuss problems, concerns and

questions, or obtain information.

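### No scheduled adverse-effect check is described for the stimulation sessions, so session-related harm in a largely sedated population may be under-recorded and not compared fairly between arms

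*Combined protocol and SAP*

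**What the plan says.** All places are in the Research Description of the combined protocol and SAP.

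- **Data and Safety Monitoring.** Among the matters the board reviews is "reporting of adverse effects by patients or nurses". The next paragraph adds: "Adverse effects will be recorded on study forms and reviewed by the DSMB". The board will consider stopping if it concludes that "excessive adverse effects clearly linked to one of the treatment arms are occurring". It may also end the study for safety or risk issues more generally. On timing: "This board will review the study at twelve month intervals". On results so far: "To date there have been no adverse events".
- **Background.** The protocol says that "many MICU patients require significant sedation and are too obtunded to realistically participate in any active exercise training regimen". It gives the purpose of the study as a safe, nonvolitional way to exercise the leg muscles.
- **Informed Consent Process.** Most ICU patients are said to receive some sedation, and next of kin alone may sign when the patient cannot.
- **Research Procedures, All Stim 2.** Current is raised until a force target is reached, and sham sessions use zero current. The support for tolerability is: "We have performed preliminary tests in normal individuals indicating that this level of force activation is well tolerated". No operator is named.
- **Research Procedures, Hospital Outcomes.** Records are reviewed twice a week for weaning, transfer, death, reintubation, length of stay and readmission.
- **Data Collection.** This field refers the reader back to the section above it and adds nothing.

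**The concern.** The harms the protocol itself names under Potential Risks, Safety Precautions and Benefit vs. Risk are largely sensations: tingling, and pain when the adhesive electrodes are removed. A sedated patient may be unable to describe either. If no one is asked to look at the skin or at pain behaviour after a session, such effects reach the study form only when someone happens to notice and report them.

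Two things are at stake. First, a record of no adverse events cannot distinguish effects that did not occur from effects that were not looked for, yet a safe form of exercise is part of the study's stated purpose. Second, the arm-linked stopping criterion needs adverse effects to be found with equal effort in the active and sham groups. Unscheduled reporting does not secure that.

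**Working it through.** **Step 1: is a session-level check described anywhere?**

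| Place | What is collected | Adverse-effect item at or after a session? |
|---|---|---|
| Quadriceps Twitch | twitch force, both legs | none |
| All Stim 2 | current setting, force target, session length | none |
| Initial Clinical Parameters | demographics, vital signs, ventilator settings, pre-hospital function | none; vital signs at the initial visit only |
| Hospital Outcomes | weaning, transfer, death, reintubation, stay, readmission | no local or session-related effect |
| Follow-up Visit (28 days) | walk distance, return to work, SGRQ | none |
| Data Collection | refers back to the above | none |
| Data and Safety Monitoring | patient or nurse reports; study forms | assessor, timing and items not stated |

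**Step 2: who can report?** Background describes many MICU patients as "too obtunded to realistically participate in any active exercise training regimen", and Informed Consent Process says most ICU patients are sedated. The first phrase concerns exercise, not reporting. That such patients often cannot describe discomfort is an inference, though a reasonable one, and the next-of-kin signature provision supports it. The tolerability tests were in people who could speak up.

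**Step 3: how much could incomplete detection matter?** The plan gives no adverse-effect rate and no numeric stopping boundary, so there is no figure to reproduce. What follows is illustration.

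Inputs from the documents: 15 enrolled; 2:1 active to sham; 24 planned, with 14-16 active. Assumed: 15 × 2/3 = 10 active so far; true per-patient rate *p* on active treatment of 10% to 30%; share detected and recorded *s* of 100%, 50% or 25%.

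Chance that no event is recorded among 10 active patients = (1 − *p* × *s*)^10:

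| True rate *p* | all detected | half | a quarter |
|---|---|---|---|
| 10% | 0.90^10 = 35% | 0.95^10 = 60% | 0.975^10 = 78% |
| 20% | 0.80^10 = 11% | 0.90^10 = 35% | 0.95^10 = 60% |
| 30% | 0.70^10 = 3% | 0.85^10 = 20% | 0.925^10 = 46% |

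At full enrolment with 16 active patients and *p* = 10%, the chance that the board sees at least one event, 1 − (1 − *p* × *s*)^16, is 0.815, 0.560 and 0.333. With 14 active it is 0.771, 0.512 and 0.298.

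**Step 4: what is due to sample size alone.** With perfect detection, zero events in *n* patients has a one-sided 95% upper limit of 1 − 0.05^(1/*n*): 18.1% for *n* = 15 and 25.9% for *n* = 10. These limits reflect small numbers and would be the same under any reporting method. They do not measure this defect. Incomplete detection widens them: for *n* = 15, 18.1%/0.5 = 36.2% if half of events are recorded.

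**The case against.** The strongest reply is that the quoted words come from a list of what the board reviews and do not define the only route. Effects are also recorded on study forms, which are not in the documents and may already contain suitable items. Sedation does not stop nurses from reporting. The research team visits until discharge, families have the investigator's contact details, the board checks data completeness, and chart review finds the major events.

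Much of this stands, and it rules out several stronger readings that a reader might infer:

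- *That the board may stop only for arm-linked effects.* The section contains no such restriction and also provides for termination on safety or risk grounds.
- *That the board would be starved of data.* Deaths, reintubations and readmissions come from records whatever the patient can say.
- *That nurses have no part in the sessions, or that the operator records nothing.* The procedures are in the passive voice and name no operator.
- *That the statement covering the first 15 patients is known to rest on passive collection.* The documents do not say how those data were gathered.

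What the reply does not supply is a stated assessor, time or item for local and patient-perceived effects. None of the listed routes is directed at them. The missing numeric threshold and the twelve-month reviews are separate limits on the stopping provision, and better collection would be needed whatever the threshold.

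**Conclusion.** The concern holds in limited form. Patient or nurse reports are the only named source, the forms have no stated assessor, timing or content, and no session-level safety observation is described. In a population the protocol calls largely sedated, skin effects, pain and discomfort may be under-recorded and unequally ascertained by arm.

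This weakens the no-adverse-events statement as support for the aim of safe exercise. It does not show that harm has occurred or that events were missed. The size cannot be measured from the documents. The 11%, 35% and 60% figures rest on an assumed 20% rate, an assumed 10 active patients and assumed detection shares, and the direction is the same across the range shown. The change should be made before recruitment resumes, since the Progress of the Research item reports that recruitment is stopped.

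**What to change.** In Research Procedures (All Stim 2) and in Data and Safety Monitoring, state that whoever applies and removes the electrodes completes one fixed line on the study form at the end of every session, identical in both arms. It should record:

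1. the skin under each electrode;
2. observed pain behaviour, or the patient's own report if awake;
3. bedside-monitor vital signs at the start and end of the session.

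Tabulate these by arm for the board, beside spontaneous reports and the events found by chart review. For the first 15 patients, say that the no-adverse-events statement was made without a scheduled session check described in the protocol.

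**Cost.** One line per session: 9 patients remaining to 24, times 7 sessions, is 63 entries. If the 12 further patients mentioned under Study Population are recruited, it is 12 × 7 = 84. No added test or visit is needed, and treatment, eligibility and the efficacy analysis are unchanged.

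**Downsides.** Minor skin findings will now be counted, so the reported rate will look less favourable. The operator may know the arm, because sham uses zero current, and that could colour the scoring of pain behaviour. The report should say so and give most weight to the objective items.

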The objective for this study is to determine if daily exercise using All-Stim 2 stimulation of quadriceps muscles will increase leg strength and improve outcomes (duration of hospitalization, long term mobility, long term disability) for mechanically ventilated MICU patients. We plan to randomize patients accepted into this protocol to administration of either sham exercise (i.e. placement of All-Stim 2 units on the legs for 30 minutes a day without activation of the electrical stimulation program) or active exercise (placement of All-Stim 2 electrodes on both legs and stimulating quadriceps muscles to rhythmically contract for 30 minutes a day). The two groups (sham and active exercise) will be treated for 30 minutes a day for seven days. The effects of exercise on quadriceps strength will be assessed by measuring quadriceps force generation (QuadTw) in response to magnetic stimulation of the femoral nerves. The QuadTw assessment will be made immediately before institution of sham or active exercise and will be repeated one day after the conclusion of the seven day training regimen. Chart review and patient follow-up will be used to determine if this treatment regimen has an impact on clinical outcome measures, i.e. duration of hospitalization, long term mobility, long term disability.

**Study Design:** Describe the study design (e.g., single/double blind, parallel, crossover, etc.). Indicate whether or not the subjects will receive placebo medication at some point in the research procedures. Also, indicate whether or not the subjects will be randomized in this study. You may reference sponsor's protocol pages and attach as an appendix in the E-IRB "Additional Information" section, however, a summary paragraph must be provided in the text box below. (Including the study design table from a sponsor's protocol is helpful to IRB members.)

*Community-Based Participatory Research:* If you are conducting [community-based participatory research \(CBPR\)](#), describe strategies for involvement of community members in the design and implementation of the study, and dissemination of results from the study.

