*Research Repositories:* If the purpose of this submission is to establish a Research Repository (bank, registry) indicate whether the material you plan to collect would or would not be available from a commercial supplier, clinical lab, or established IRB approved research repository. Provide scientific justification for establishment of an additional repository collecting duplicate material. Describe the repository design and operating procedures. For relevant information to include, see the UK Research Biospecimen Bank Guidance [\[PDF\]](#) or the UK Research Registry Guidance [\[PDF\]](#)

The basic study design is to:

- (a) obtain informed consent;
- (b) measure magnetic stimulated quadriceps twitch (QuadTw) strength bilaterally;
- (c) randomize patients to treatment with either:

Sham therapy, consisting of bilateral placement of All-Stim 2 electrodes for 30 minutes a day without activation of the electrical circuitry of the unit, or

Active therapy, using the All-Stim 2 electrodes to actively produce a rhythmic quadriceps contraction for 30 minutes a day.

We plan to have a total of 24 patients in the study, with two patients randomized to active treatment for every one patient given sham treatment. As a result we anticipate the final group studied will include 14-16 active treatment patients and 6-8 sham treatment patients.

- (d) continue these regimens daily for 7 days;
- (e) remeasure magnetic stimulated QuadTw on day 8;
- (f) the research team will visit the patient until discharge and will record duration of mechanical ventilation, duration of ICU stay, and total duration of hospitalization; and,
- (g) patients will be visited by a member of the research team at 28 days after study entry to assess the distance that can be walked in 6 minutes (i.e. the 6 minute walk test) and to assess patient well being using the St. Georges Research Questionnaire (SGRQ, a commonly used and extensively validated instrument to assess patient well being).

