#### *Research Repositories*

If the purpose of this submission is to establish a research repository describe the informed consent process. For guidance regarding consent issues, process approaches, and sample language see the Sample Repository/Registry/Bank Consent Template [\[PDF\]](#)

After reviewing the study with the patient and their family, the PI and/or [name] will ask the patient and the family if they wish to participate. The consent form will be reviewed with the patient and their family detailing the risks associated with the planned measurements. If the patient and family agree, the consent form will be signed. If the patient and their family wish they can think about the study and the PI will return the next day. After the consent form is signed, QuadTw measurements will be performed the same day and All-Stim 2 therapy will be started. The PI ([name]) or [name] will obtain all informed consents for the study. To eliminate coercion, all families and study recipients will be told that refusal to participate will in no way influence their care while at the University of Kentucky. Consent will be documented by having both the patient and the next of kin sign the consent form. Because most ICU patients receive some form of sedation, it is the intent of the PI to always inform the family as well as the patient and always have the family member with decision making power over the patient's care (e.g. their spouse or family member with power of attorney) sign the consent form. We will always seek to have the patients also sign the consent form. Under certain circumstances the patient may be so disabled that signage of the consent form is not possible (e.g. the patient is sedated or both hands are instrumented with IV's and pressure transducers). In the event of mental or physical inability of the patient to sign the consent form, the next of kin alone will sign the form.

[Back to Top](#)

**Research Procedures:** Describe the research procedures that will be followed. Identify all procedures that will be carried out with each group of subjects. Differentiate between procedures that involve standard/routine clinical care and those that will be performed specifically for this research project.

It will first be verified that the patient does not meet any exclusion criteria and that informed consent has been obtained.

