**Hospital Outcomes:** After recruitment into studies, electronic hospital records will be reviewed twice a week to determine the time from the point of initial study measurements to successful weaning from mechanical ventilation (defined as remaining off all mechanical ventilation for more than 4 days). Alternative outcomes that will be recorded, for patients that are not weaned from mechanical ventilation, include transfer to a chronic facility for long term weaning from mechanical ventilation (i.e. an LTAC) or death. Deaths will be further subclassified as death due to withdrawal of care and death due to progression of disease. We will also record total ICU stay, total days of hospital stay, and incidence of recurrent respiratory failure, defined as a requirement for reintubation either during the initial hospitalization or at any time out to day 28 after entry into the study. We will also record hospital readmission rates.

**Follow-up Visit (28 days).** At follow-up visits we will assess the distance walked in 6 minutes and we will ask patients if they have returned to work (either full time or part time). We will also have patients fill out the St. Georges respiratory questionnaire (SGRQ) on return visits. This questionnaire evaluates patient's perceptions about their respiratory health, including their assessment of the ability to perform simple tasks of daily living. The PI and/or [name] will visit the patient's domicile (or other site of habitation) to obtain these assessments.

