The PI has studied various aspects of respiratory muscle function and dysfunction over a 25 year period. During this time, the PI has published approximately 100 peer reviewed papers on original research related to respiratory muscle and other critical care topics, as well as 150 abstract presentations at national meetings.

The PI is currently funded by an NIH grant as PI and also receives support as a co-investigator from another NIH grant held by [name]. The PI's laboratory is equipped with a cart containing all the apparatus required to obtain QuadTw measurements. Specifically, the cart is equipped with two MagStim 200 magnetic stimulators equipped with dual figure of eight coils for nerve stimulation, the quad board used for positioning the leg, and a force transducer with a computer interface. This cart is mobile and can be moved to the ICU rooms when needed to assess leg strength. The cart is equipped with sterile wipes that will be used to disinfect all exposed surfaces before and after entrance and exit from patient rooms. Both the Magstim and All Stim 2 units are FDA approved and are in common usage in the USA and other countries for assessment of neurological function and quadriceps conditioning, respectively.

**Potential Risks:** Describe any potential risks or likely adverse effects of the drugs, biologics, devices or procedures subjects may encounter while in the study. Please describe any physical, psychological, social, legal or other risks and assess their likelihood and seriousness.

Use of magnetic twitch stimulation for femoral nerve stimulation is essentially painless. Use of the All-Stim 2 device produces a mild tingling sensation but is also essentially painless at the settings we will use. Removal of the All-Stim 2 electrodes, which have sticky adhesives on their inner surface, could theoretically cause pain in a very hairy individual (this will be dealt with as described below). Both devices could theoretically produce problems in individuals with pacemakers or implanted defibrillators, so patients with these devices will be excluded from the study. We will ask patients to perform a six minute walk test at 28 days after discharge and use a pedometer to assess distance walked. This test has been previously used to assess patient outcomes after ICU discharge (see references 1, 2) with no reported complications. There is essentially no risk to performance of chart reviews or evaluation using the SGRQ.

[Back to Top](#)

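### QuadTw results are promised to patients and families without being held until after the 28-day walk, SGRQ and work question

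*Combined protocol and SAP*

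**What the plan says.** The promise is in the Research Description under Subject Complaints: "We will provide the patient and his family any information obtained from the QuadTw measurements". The same sentence adds that the team "will provide them with information as to whether the measured numbers are normal or reduced". It does not say when this happens, does not separate the baseline result from the day-8 result, and sets no hold until follow-up is complete.

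There are two measurements. The baseline one is described under Informed Consent Process: "After the consent form is signed, QuadTw measurements will be performed the same day and All-Stim 2 therapy will be started". The second is step (e) of the Study Design: "remeasure magnetic stimulated QuadTw on day 8".

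The follow-up outcomes come later. Study Design step (g) says "patients will be visited by a member of the research team at 28 days after study entry to assess the distance" walked in six minutes, and to administer the SGRQ. Research Procedures, under the 28-day follow-up visit, adds a question on return to work and describes the SGRQ: "This questionnaire evaluates patient's perceptions about their respiratory health". Potential Risks dates the walk differently: "We will ask patients to perform a six minute walk test at 28 days after discharge".

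The comparator is a sham, described in the Objectives as "placement of All-Stim 2 units on the legs for 30 minutes a day without activation of the electrical stimulation program". No section states that patients, families or assessors are blinded.

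**The concern.** The change in QuadTw from baseline to day 8 is the strength effect that the trial sets out to test. Under the rule as written, a patient or family may learn it before the 28-day visit. The measures taken at that visit depend on effort (the walk) or on the patient's own account (the SGRQ and the work question). Long-term mobility and disability are named in the Objectives, so these measures bear on a stated aim.

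If stimulation raises QuadTw, patients on active treatment would tend to hear better numbers than patients on sham. A better walk or SGRQ score in the active arm could then come partly from encouragement and partly from stronger legs. Nothing in the protocol or the SAP would separate the two. The risk is greatest in the scenario that the investigators hope for.

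**Working it through.** The documents give no figure for this point to reproduce. The check is a timeline plus simple arithmetic on the QuadTw values in the Background.

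**1. Time available for disclosure.** QuadTw is complete on day 8.
- If the visit is 28 days after study entry (Study Design), the gap is 28 − 8 = 20 days.
- If it is 28 days after discharge (Potential Risks), and discharge is no earlier than day 8 (an assumption), the gap is at least 28 days.

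On either anchor both QuadTw results exist before the walk.

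**2. Which part of the disclosure could differ by arm.** The Background gives a mean twitch of 12 N, with an unlabelled spread of 4, in ventilated patients, and 38 N in healthy adults.
- 12/38 = 31.6%, which agrees with the stated 32% of normal.
- If the 4 is a standard deviation (an assumption), the healthy mean lies (38 − 12)/4 = 6.5 SD above the patients' mean.
- The table gives the normal-tail probability that a patient reaches 38 N, at baseline and after an assumed 50% gain (mean 18 N). SDs above 4 N are assumed, in case the 4 is not an SD.

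| SD (N) | At or above 38 N, mean 12 N | At or above 38 N, mean 18 N |
|---|---|---|
| 4 | 4 × 10⁻¹¹ | 3 × 10⁻⁷ |
| 8 | 0.06% | 0.6% |
| 12 | 1.5% | 4.8% |
| 16 | 5.2% | 10.6% |

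The plan gives no cut-off for normal. A cut-off below the healthy mean would raise these figures. On this reading, nearly everyone in both arms would be told that the value is reduced, so the label carries little information about the arm. What could differ by arm is the pair of values, and so the change.

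**3. Who an amendment can reach.** Subject Info To-Date and the Introduction report 15 enrolled against a target of 24, which leaves 24 − 15 = 9. Study Population plans a further 12, but 15 + 12 = 27 exceeds the target. The two figures do not agree.

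**4. Which outcomes are exposed.** QuadTw is a magnetically evoked twitch that needs no effort from the patient, and it is finished on day 8, so later expectation cannot alter it. The walk, the SGRQ and the work question are exposed.

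**The case against.** The strongest reply is that allocation is already easy to guess. Active treatment makes the quadriceps contract and tingle for 30 minutes a day over seven days, while the sham delivers no current. Awake patients and families at the bedside may infer the arm well before day 8, and no blinding is claimed. This largely stands. A reader might infer that the disclosure rule defeats the sham, but the documents do not support that: most of the expectation problem would remain with the rule removed. Disclosure is nonetheless a separate route. The Background says many of these patients are heavily sedated, and the consent section provides for next of kin to sign alone. A patient who did not perceive the stimulation can still be told the change later, when awake. The change also conveys personal response, which is more than allocation.

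Second, both arms fall under the same rule. That stands too: if stimulation does not affect QuadTw, this route would not be expected to favour either arm.

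Third, the sentence answers a form prompt that covers complaints and requests for information, so it may describe replies to requests rather than routine reporting on day 8. A reader might infer that results are handed over at once. The text gives no timing, so that cannot be stated as fact. What can be stated is that nothing holds them back.

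Fourth, returning individual results is a legitimate choice, and the IRB form asks for a disclosure plan or a justification for not disclosing health-relevant findings. That prompt does not bar a delay.

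**Conclusion.** The point holds as a possible and avoidable source of bias in the 28-day walk, SGRQ and work question. It requires three things: that results are given before the visit, that QuadTw responds to treatment, and that knowing the change affects effort or self-report. The documents establish none of these, and the size of any shift cannot be derived from them.

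Three wider inferences are not supported. The QuadTw comparison is not affected by this route. A path through families to ward staff, and so to mobilisation or discharge, is speculation, because no section says that families relay results or that staff act on them. And although the promise covers all 24 patients, an amendment cannot protect all of them: 15 are already enrolled, and patients who die before the visit contribute no walk or SGRQ.

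The point still merits an amendment because closing the route costs little.

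**What to change.** Amend the Subject Complaints text so that QuadTw results are given to the patient and family after the 28-day assessments are complete, or after death or withdrawal. Make the same change in the consent form if it repeats the promise; its text is not available here, so this cannot be checked.

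Reconcile the 28-day anchor (study entry in Study Design, discharge in Potential Risks) so that the hold has a defined end. Reconcile the number still to be enrolled (9 or 12).

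For the 15 patients already enrolled, record whether and when each QuadTw result was disclosed, so that the report can describe the exposure.

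The cost is a short amendment, possibly with a justification to the IRB for the delay, while recruitment is already paused. Families would wait about three to four weeks, counting from study entry, for a research measurement. The baseline twitch is used to set the stimulation current, but that does not depend on telling the family, and no section uses the disclosed result to guide care.
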